4. JUSTIFICATION AND OBJECTIVE OF THE CLINICAL TRIAL

FMT for ADP is a promising approach, given the documented role of bacteria in the pathogenesis of this condition. However, whereas a single FMT in patients with C. difficile colitis seems to be sufficient to achieve a high therapeutic success rate, an intensified therapy with daily or repeated FMT to firmly establish the donor microbiome in the recipient appears to be the therapy of choice in patients with chronic intestinal inflammation (as outlined above). However, repeated endoscopic FMT is costly and not feasible. An alternative therapeutic modality is the repeated application of FMT via enemas. But this approach is suboptimal due a) patient preferences (oral> rectal), b) the occurrence of severe rectal pain during the application in patients with concomitant cuffitis and c) problems with retention of the enema content.⁵⁸⁻⁶⁰ Thus the optimal approach is a combination of endoscopic FMT and consecutive therapy with oral FMT to help establish the donor microbiome in the host. With the recent availability of capsulated FMT this approach became feasible. The objective of this proof of concept trial is to evaluate the safety of endoscopic followed by oral FMT in patients with ADP and to estimate the effect size to be achieved from FMT therapy in patients with ADP for subsequent evaluation in a large definitive trial. A secondary objective is to study the microbial engraftment of donor FMT in the recipients.

Specific hypothesis

We hypothesize that FMT is a novel therapeutic option for patients ADP. This form of pouchitis is predestined to benefit from FMT, since bacterial dysbiosis, which can only be controlled with antibiotics, appears to be the major driver of the clinical symptoms. We choose two distinct outcomes, a clinical and translational aim, to investigate the effect of FMT in patients with ADP.

Aim 1: Evaluation of safety, tolerability and clinical effectiveness (measured as clinical response or remission and discontinuation of antibiotic therapy) of FMT in patients with ADP.

Aim 2: Evaluation of the impact of FMT on the fecal bacterial microbiome in patients with ADP, which will provide functional data about possible mechanisms of this therapy.

• Safety profile of fecal transplant

Fecal transplant has an excellent safety profile in patients with C. difficile colitis. Also FMT for C. difficile colitis seems to be safe in immunocompromised patients.

In patients with IBD often mild flu symptoms after transplant have been observed.⁵¹ However, these are only transitory and no organ failure or organ toxicity has been reported.

• Choice of Study Drug Dosage

The endoscopic FMT is an established method in patients with C. difficile colitis. The advantage of endoscopic rather than enema applied FMT is the possibility to install the FMT proximal to the pouch, which facilitates mucosal contact of the FMT not only in the pouch but also in the distal terminal ileum. However a single application most likely leads to an incomplete engraftment of the donor microbiome and repeated FMT is likely to have superior results as shown in several uncontrolled observations as well as in a large placebo controlled trial in patients with ulcerative colitis and a case series of 5 ADP patients.^{45, 49, 51, 61} Repeated endoscopic FMT is not a feasible option. Oral FMT has been recently established and seems to have slightly inferior efficacy in patients with C. difficile colitis compared to endoscopic FMT.^{53, 55, 56} Daily FMT using enema is another alternative, but in our opinion is suboptimal due to patient preferences, often pain during application of the enemas due to concurrent cuffitis and problems with retention in the setting of enema therapy.⁵⁸⁻⁶⁰ Oral FMT offers the possibility to a superior engraftment and maintenance of the donor microbiome over longer time periods.⁵⁸ However, no data about such an approach are yet available. The only available data for patients with pouchitis and FMT are based on single FMT or repeated endoscopic FMT as outlined above.

5. TRIAL ENDPOINTS

• Primary Endpoint:

Safety and Tolerability of FMT

• Number of study patients, who discontinued therapy

- Adverse events grouped by body system
- Changes in laboratory values
- Secondary Endpoints
- Clinical remission (mPDAI score ≤ 4 points) and no need for antibiotic therapy at week 4.
- Clinical remission (clinical mPDAI score ≤ 4) and no need for antibiotics at week 8*.
- Clinical remission (clinical mPDAI score ≤ 4) and no need for antibiotics at week 16*.
- Endoscopic improvement of active pouchitis (decrease from baseline in mPDAI endoscopic subscore ≥ 2 points) at week 4.
- Response: Symptomatic improvement of active pouchitis (decrease from baseline in mPDAI clinical subscore ≥ 2 points) and no need for antibiotic therapy at week 4.
- Response: Symptomatic improvement of active pouchitis (decrease from baseline in mPDAI clinical subscore ≥ 2 points) and no need for antibiotic therapy at week 8*.
- Response: Symptomatic improvement of active pouchitis (decrease from baseline in mPDAI clinical subscore ≥ 2 points) and no need for antibiotic therapy at week 16*.

*Only patients who do not continue in open label extension

- Exploratory analyses (OL=Open label):
- Endoscopic improvement of active pouchitis (decrease from baseline in mPDAI endoscopic subscore ≥ 2 points) at in open label extension week 8.
- Clinical remission (mPDAI score ≤4 points and a decrease in the baseline mPDAI> 2 points) and no need for antibiotic therapy at week 10 OL.
- Clinical remission (clinical mPDAI score ≤ 4) and no need for antibiotics at week 14 OL.
- Clinical remission (clinical mPDAI score \leq 4) and no need for antibiotics at week 22 OL.
- Response: Symptomatic improvement of active pouchitis (decrease from baseline in mPDAI clinical subscore ≥ 2 points) and no need for antibiotic therapy at week 10 OL.
- Response: Symptomatic improvement of active pouchitis (decrease from baseline in mPDAI clinical subscore ≥ 2 points) and no need for antibiotic therapy at week 14 OL.
- Response: Symptomatic improvement of active pouchitis (decrease from baseline in mPDAI clinical subscore ≥ 2 points) and no need for antibiotic therapy at week 22 OL.
- Symptomatic worsening of active pouchitis (decrease from baseline in mPDAI clinical subscore ≥ 2 points) from FMT week 0 week 16
- Quantitative changes in mPDAI from baseline values
- Quantitative changes of calprotectin from baseline
- Alterations in stool microbiome after FMT
- Engraftment of donor FMT
- Alterations in stool microbiome before and after FMT in study patients with antibiotic dependent pouchitis

Since the bacterial dysbiosis in the pouch plays an important role in the pathogenesis of pouchitis a secondary endpoint is the evaluation of the fecal microfloral pattern by 16S rDNA collected before and 2,4,8 and 16 weeks after FMT.

• Evaluation of calprotectin as a marker of pouch inflammation before and after FMT Repeated pouchoscopies to evaluate the degree of pouch inflammation are not feasible. Also due to safety concerns, biopsies of the pouch will not be taken before FMT. Calprotectin, a member of the S100 family of calcium-binding proteins is abundant in the stool and its level correlates with the endoscopic degree of intestinal inflammation in patients with ulcerative colitis and pouchitis. ^{62, 63} Calprotectin can be readily quantified in feces using enzyme-linked immunosorbent assay (ELISA) or an immunoassay. We will collect stool samples for the measurement of calprotectin at the screening visit and on weeks 2, 4, 8 and 12 after FMT.

6. STUDY DESIGN

• Study Population

The study will include 20 patients who have undergone total proctocolectomy and ileal pouch-anal anastomosis (IPAA) for ulcerative colitis (UC). The study patient qualifies for the study if he/she has episode of active pouchitis, defined as a mPDAI \geq 5 and a history of > 3 antibiotic therapies for pouchitis in the last 12 months or if he/she is in need for chronic antibiotic therapy to maintain clinical remission and has history of at least 2 attempts in the last 24 months to stop continuous antibiotic therapy resulting in pouchitis episodes.

• Treatment period.

2 weeks of FMT/ placebo therapy followed by evaluation of clinical and endoscopic outcome at week 4, and clinical evaluation at week 8 and 16. In case the study patient does not achieve clinical remission at week 4 or experiences a flare of disease on day 15-28 after start of the study he/she will be offered the possibility to participate in open label extension with an additional endoscopic FMT followed by 2 weeks of oral FMT and clinical follow up at week 4, 8 and 16.

- Inclusion Criteria
- Signed informed consent.
- Man or woman between 18 and 70 years of age.
- IPAA after colectomy for ulcerative colitis
- The subject has been diagnosed with one of the following 2 pouchitis subtypes:
 - Active pouchitis, defined as a mPDAI \geq 5 and a history of \geq 4 antibiotic therapies for pouchitis in the last 12 months

or

Need for ongoing antibiotic therapy (> 4 weeks) to maintain clinical remission and a history of at least 2 attempts in the last 24 months to stop antibiotic therapy resulting in pouchitis episodes. Concomitant oral 5 ASA or local therapies containing 5-ASA (enemas, suppositories) or steroid enemas are permitted but not required but have to be stable for 4 (oral) or 2 weeks (topical) before inclusion in the study.

- Exclusion criteria
- Treatment with biologics (e.g. infliximab, adalimumab, golimumab, vedolizumab)
- Treatment with immunomodulators (azathioprine, 6-MP, methotrexate), steroids or any investigational drugs
- Use of cholestyramine
- Crohn's disease of the pouch
- Known cytomegalovirus infection of the pouch
- Clostridium difficile infection
- Isolated moderate or severe cuffitis
- Clinical significant strictures of the pouch inlet or outlet
- Concurrent intestinal obstruction
- History of familial adenomatous polyposis
- History of uncontrolled lactose intolerance
- History of confirmed (serological test and/or histology) celiac disease
- Pregnancy, breast feeding, or planning to become pregnant during the trial
- Non steroidal inflammatory medications (NSAIDs) as long-term treatment, defined as use for at least 4 days a week each month
- Dysphagia (oropharyngeal, esophageal, functional, neuromuscular)
- History of recurrent aspiration episodes
- Proven gastroparesis
- Allergy to the following generally regarded as safe ingredients (GRAS): glycerol, acid resistant HPMC, gellan gum, cocoa butter, titanium dioxide
- Adverse event attributable to previous FMT
- Allergy/intolerance to pump inhibitor therapy
- Any condition for which the investigator thinks the FMT treatment may pose a health risk (e.g. severely immunocompromised)
- Participation in another clinical trial within the last 30 days, simultaneous participation in another clinical trial, or previous participation in this trial
- During the trial period until one week after the trial end: Non-use of appropriate contraceptives in females of childbearing potential (e.g. condoms, intrauterine device {IUD}, hormonal contraception, or other means considered adequate by the responsible investigator) or in males with a child-fathering potential (condoms, or other means considered adequate by the responsible investigator during treatment
- Well-founded doubt about the patient's cooperation
 - Concomitant Medications

All antibiotic therapies have to be stopped 1 day before FMT.

Following drug groups are permitted as concomitant medication:

- Orally administered mesalazine containing drugs should be stable for the last 4 weeks
- Local therapies containing 5-ASA (enemas, suppositories) or steroid enemas should be at a stable dose 2 weeks before inclusion in the study.

Following drug groups are **not** permitted as concomitant medication:

- Antibiotic therapy for treatment of pouchitis
- Cytostatics/immunosuppressants, cyclosporine, tacrolimus, mycophenolate mofetil.
- Anti-TNF therapies or anti-adhesion therapy.
- Non steroidal anti-inflammatories (NSAIDs) as long-term treatment, defined as use for at least 4 days a week each month

7. OVERVIEW OF TRIAL SEQUENCE

See also study flow chart in appendix as well as study visit charts in appendix.

The trial will begin with the **screening visit (days -14 to 0).** The investigator will ask patients who are interested in participating in the study after a careful explanation, to sign an informed consent form prior to study specific examinations. The study patient will receive a copy of the consent form, which outlines the sequence of events in brief and summarizes the advantages and disadvantages of participation in the study.

After the patient has given his/her written consent, the screening examination will be performed to evaluate whether the patient is probably eligible for the study.

At the screening visit, a complete history will be taken including concomitant medication and demographic data will be collected. A physical examination will be performed and vital signs will be documented. Blood samples (max. 20 ml) will be taken from the study patient (all study patients: hematology, serum chemistry, creatinine, female study patients: urine samples for pregnancy test). Also the study patient will be provided with a stool collection kit to provide a stool sample, which should be collected at this visit or before the week 0 visit. This stool kit will also contain a sample kit for C. difficile toxin. The study patient will also be provided with a diary, which he/she will be asked to complete the diary every day in the evening during the trial. It will be also evaluated if the patient is able to swallow the oral FMT test capsule.

At least 10 days before the planned endoscopic FMT at week 0 all patients will be started on antibiotic therapy as standard of care for treatment of pouchitis. Patients on continuous antibiotic therapy will continue their regimen. Since all patients must fulfil the criteria for antibiotic pouchitis, the antibiotic with the best efficacy to treat the pouchitis episodes in the past will be used. In patients on chronic antibiotic therapy to prevent pouchitis recurrence the antibiotic regimen will be continued. 24 hours before the planned FMT the antibiotic will be discontinued.

Placebo-controlled trial period

At week 0 visit the study patient will have a physical exam and a urine pregnancy test. The patient's AE and symptom diary should be reviewed and the clinically modified PDAI calculated. The patient's concomitant medications will be reviewed. If the study patient fulfils all inclusion criteria and does not have an exclusion criterion the study patient will be randomized to either the placebo or the FMT group and a unique study ID number will be assigned, which will appear on all medication packs.

The study patient then undergoes a pouchoscopy for evaluation of the pouch inflammation and to rule out complications in the pouch structure (e.g. strictures, isolated cuffitis, which would lead to exclusion of the trial). If all inclusion criteria are met during an endoscopically guided placebo or real FMT will be performed. Additionally, the study patient will be started on omeprazole 20 mg (1 tablet/daily) as

long as he/she undergoes oral FMT or placebo therapy. The study patient will receive 2 diaries, which need to be filled out on a daily basis, the stool diary and the adverse event diary. The stool diary should be daily completed either until Visit 8 or if the patient participates in the open label extension until visit 12OL. The adverse event diary has to be daily completed until visit 6 or visit 10OL.

At visits 2 and 4 (phone visits) the coordinator will ask the study patient if adverse events occurred and will review the adverse event diary with the study patient. The coordinator will also evaluate the clinical components of the mPDAI of the last 3 days before the phone call (stool frequency, rectal bleeding, fecal urgency/ abdominal cramping, fever) as well as the concomitant medications.

Visit 3 (site visit) the coordinator will review the adverse event diary with the study patient, and will assess the mPDAI and concomitant medication. The patient will also bring a stool sample for the stool bank, which was collected earliest on day 1 after the end of the oral or placebo FMT period.

At phone visit 4 the coordinator will ask the study patient if adverse events occurred and review the adverse event diary. The coordinator will evaluate the clinical components of the mPDAI of the last 3 days before the phone call (stool frequency, rectal bleeding, fecal urgency/ abdominal cramping, fever) as well as the concomitant medications. If the patient is in remission according to the diary (mPDAI \leq 4) and is on no concomitant medications, a pouchoscopy will be planned for site visit 5. If the study patient is not in remission (mPDAI \geq 4) or had an early relapse after FMT the open label extension will be offered and the patient can be started on oral antibiotics again. For safety analyses a site visit 5 should be planned in the following 3-4 days. If the study patient chooses not to participate, he should be followed according the same schedule as patients who are in remission.

Early termination visit due to flare on day 1-28 after FMT or due to adverse event or patient unwillingness to continue in study necessitating early termination

If at any time between day 1-28 after endoscopic FMT the patient experiences recurrence of his pouchitis symptoms, he/she will contact the coordinator. The coordinator will ask the study patient if adverse events occurred and review the adverse event diary. The coordinator will evaluate the clinical components of the mPDAI of the last 3 days before the phone call (stool frequency, rectal bleeding, fecal urgency/ abdominal cramping, fever) as well as the concomitant medications.

If the study patient has active disease (mPDAI>4), an early termination study visit will be scheduled. A physical exam will be completed and, if possible, stool will be collected before the start of antibiotic therapy as standard of care. Blood labs will also be collected. The patient will be started on the same antibiotic, which he was on before entering the study. At the study visit the coordinator will review possible adverse events, evaluate the clinical components of the mPDAI of the last 3 days before the visit (stool frequency, rectal bleeding, fecal urgency/ abdominal cramping, fever) as well as the concomitant medications. If the patient wants to proceed into the open label study, he has to undergo at least 10 days of standard of care antibiotic therapy, before he can undergo the open label therapy with FMT (endoscopic and oral FMT).

If the patient is not willing to continue in the open label part of the study, he/she will be followed in the regular arm with visits 6-9.

Study visits for patients at remission at phone visit 4 and site visit 5

Phone visit 6 will evaluate for adverse events and review the adverse event diary. At this point (4 weeks after stopping the oral FMT) the patient can stop filling out the daily adverse event diary. However, the patient will be reminded to bring the completed adverse event diary to site visit 7. Additionally, the mPDAI will be calculated and the concomitant medications will be assessed.

Site visit 7 will collect all pages of the adverse event diary, and review the adverse events, which occurred since visit 6. A physical exam and blood tests will be performed and the mPDAI will be calculated. The concomitant medications will be assessed. A stool sample will be collected from the patient.

Site visit 8 will review new adverse events, concomitant medications and the mPDAI score. A stool sample will be collected from the patient.

On the last phone visit 9 the coordinator will review serious adverse events only, which may have occurred since visit 8.

Open label extension period

After at least 10 days of antibiotic therapy a pouchoscopy and FMT will be performed at site visit 6OL. A physical exam will be completed, adverse events and concomitant medications reviewed. Female patients will provide a urine sample for a pregnancy test before FMT. Similar to the previous FMT the study patient will be started on omeprazole 20 mg (1 tablet/daily) as long as he/she undergoes oral FMT therapy.

In phone visit 7OL the coordinator will ask the study patient if adverse events occurred, review the adverse event diary, and will evaluate the clinical components of the mPDAI of the last 3 days before the phone call (stool frequency, rectal bleeding, fecal urgency/ abdominal cramping, fever) as well as the concomitant medications.

At site visit 8OL the study coordinator will ask the study patient if adverse events occurred, review the adverse event diary, and will evaluate the clinical components of the mPDAI of the last 3 days before the visit (stool frequency, rectal bleeding, fecal urgency/ abdominal cramping, fever) as well as review the concomitant medications. The coordinator will collect the stool sample from the patient, which should be collected 1-3 days after the end of the oral FMT therapy .

The 9OL site visit will review adverse events and the adverse event diary, collect safety blood labs, perform a physical exam and calculate the mPDAI. A stool sample for the stool bank will be collected from the patient. A pouchoscopy will also be performed.

Phone visit 10OL will evaluate for adverse events and review the adverse event diary. At this point 4 weeks after stopping the oral FMT the patient can stop filling out the daily adverse event diary The patient will be reminded to bring the filled out adverse event diary to site visit 11OL. Additionally, mPDAI will be calculated and the concomitant medications will be assessed.

Site visit 110Lwill collect all pages of the adverse event diary, and review the adverse events, which occurred since visit 100L. A physical exam and blood tests will be performed and the mPDAI will be calculated. The concomitant medications will be reviewed. A stool sample for the stool bank will be collected from the patient.

Site visit 12OL will review new adverse events, concomitant medications and the mPDAI score. A stool sample for the stool bank will be collected from the patient.

On the last phone visit 13OL the coordinator will review serious adverse events only, which may have occurred since visit 12OL.

Study patients experiencing a recurrence of symptoms in the open label extension period

If the study patient is experiencing worsening of disease after the second FMT, antibiotic therapy will be re-initiated as a standard of care approach. The patient will nevertheless be followed up according to the same schedule as patients not experiencing a relapse.

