8. SCREENING VISIT AND STUDY VISITS 1-4

- Site screening visit
- Data to be recorded:

General parameters:

Initials

Date of birth

Sex

Smoker (yes/no/ex-smoker)

Race (NIH categories)

Ethnicity (NIH categories)

Case history

Date of confirmation of the diagnosis

Classification of UC before IPAA (proctitis, left sided colitis, pancolitis)

Type of extraintestinal symptoms

Specific therapies for pouchitis within the last year

Type of medication

Specific therapies for pouchitis within the last 4 weeks

Type of medication

Examinations

Vital signs: blood pressure (mm Hg), heart rate (min⁻¹), weight (kg), calculation of BMI, temperature

Height (cm)

Physical examination:

- Head (including ENT and eyes)
- Lymphatic system
- Endocrine system
- Lungs and respiratory tract
- Peripheral vascular system
- Cardiovascular system

- Gastrointestinal tract, liver, spleen
- Urogenital system
- Nervous system
- Muscular and skeletal system
- Skin and connective tissue
- Other

each: actual status: Present finding / normal condition / not examined

Blood sampling and measurement of laboratory parameters

- Hematology
- Serum chemistry
- Urine pregnancy test
- Stool sample for C. difficile toxin

Formal aspects:

Informed consent procedure

Verification of inclusion / exclusion criteria (eligibility check), as far as possible

Dispense stool collection kit for stool sample (stool sample should be brought back at visit week 0)

Explain and distribute stool diary to study patient

Perform test if patient is able to swallow an empty FMT test capsule

• Visit 1: Site visit week 0

Examinations

Vital signs: blood pressure (mm Hg), heart rate (min-1), weight (kg), temperature

Physical examination:

- Head (including ENT and eyes)	- Gastrointestinal tract, liver, spleen
- Lymphatic system	- Urogenital system
- Endocrine system	- Nervous system
- Lungs and respiratory tract	- Muscular and skeletal system
- Peripheral vascular system	- Skin and connective tissue
- Cardiovascular system	- Other

each: actual status: Present finding / normal condition / not examined

Blood sampling and measurement of laboratory parameters (must be performed in the 24 hours before *FMT*)

- Urine pregnancy test

Dispense stool collection kit for stool sample (stool sample should be brought back at visit week 2)

Formal Aspects:

Calculation of the mPDAI

Verification of inclusion / exclusion criteria (eligibility check)

Randomization

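### The one pre-FMT stool sample may be taken before or during the antibiotic lead-in, so calprotectin and microbiome changes start from baselines in different treatment states

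*Combined protocol and SAP*

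**What the plan says.** **The sample.** Section 7 provides a stool kit at screening, for a sample "which should be collected at this visit or before the week 0 visit". Section 8 has the kit dispensed at screening and says "stool sample should be brought back at visit week 0". Section 5 is narrower for one marker: "We will collect stool samples for the measurement of calprotectin at the screening visit". Section 20 (Microbiome Analyses) plans one sample per patient before transplant. The chart in Section 21 marks stool at screening and next at visit 3, with none at visit 1. Its footnote assigns the screening sample to microbiome, calprotectin and C. difficile.

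**The antibiotic.** Section 7 places screening between day −14 and day 0 and states: "At least 10 days before the planned endoscopic FMT at week 0 all patients will be started on antibiotic therapy". For those already treated, "In patients on chronic antibiotic therapy to prevent pouchitis recurrence the antibiotic regimen will be continued". For everyone, "24 hours before the planned FMT the antibiotic will be discontinued".

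**The patients.** The inclusion criteria in Section 6 admit two groups: "The subject has been diagnosed with one of the following 2 pouchitis subtypes". One is active pouchitis with repeated antibiotic courses in the past year; the other is a need for ongoing antibiotics.

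**The use.** Sections 5 and 20 list calprotectin change from baseline and microbiome alteration after FMT as exploratory. The text of Section 5 nevertheless calls the microbiome evaluation secondary, and Section 20 (Clinical analyses) calls calprotectin change secondary. Section 20 describes summaries for all 20 subjects and for subgroups.

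**The concern.** A change from baseline is interpretable only if the baseline means the same thing in every patient. Here, one active-pouchitis entrant may give stool in untreated disease and another after many days of an antibiotic chosen because it has worked before. Later samples are planned off antibiotics.

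Section 5 presents calprotectin as a marker of pouch inflammation, and Section 2 describes antibiotics as effective in pouchitis. If a patient's baseline precedes the antibiotic, part of any later fall may belong to the lead-in. In a summary over all patients, that part would be read together with the effect of FMT.

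At stake is the interpretation of the calprotectin and microbiome results, the latter being Aim 2 in Section 4. The primary safety endpoint and the remission endpoints are not involved.

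**Working it through.** **1. The plan's own figures.** Section 20 counts stool samples as 9×4 = 36 plus 11×7 = 77. These sum to 113; the text states 116. The schedule described in words gives 1+2+2 = 5 per remission patient and 1+2+4 = 7 per open-label patient, so 9×5 + 11×7 = 122. Whichever total is intended, the described schedule has one pre-transplant sample per patient. The power figure (80% for 10% versus 77.5%, 10 per arm, two-sided Fisher test at 0.05) reproduces at 80.2% by exact enumeration. It concerns remission and is untouched by this point.

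**2. The two timelines** (Section 7 and the Section 21 chart).

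| Event | Day relative to FMT |
|---|---|
| Earliest baseline stool | −14 |
| Antibiotic start, if not already on one | −14 to −10 |
| Antibiotic stop | −1 |
| Latest baseline stool | 0 |

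A pre-antibiotic sample is possible over at most 14 − 10 = 4 days, and that stretch includes a screening visit held on day −14. A later sample can follow up to 14 − 1 = 13 days of treatment. Chronic-antibiotic patients are on treatment throughout.

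**3. Other measurements are tied down.** Section 19 takes the baseline clinical mPDAI from the three days before week 0. Section 8 gives the week 2 and week 4 stools windows of days 15–17 and 25–27. At a flare, Section 7 asks for stool before antibiotics restart if possible. The baseline stool has no such rule.

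**4. Scale (assumed inputs).** Let q be the share of all baselines taken on antibiotics and s the antibiotic's shift of the marker in SD units. Relative to an end-of-lead-in baseline for everyone:

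- shift in mean change = (1 − q)s
- added variance = q(1 − q)s²

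| s | Shift, q = 0 | Shift, q = 0.5 | Shift, q = 1 | Added variance, q = 0.5 |
|---|---|---|---|---|
| 0.25 | 0.25 | 0.125 | 0 | 0.016 |
| 0.5 | 0.5 | 0.25 | 0 | 0.063 |
| 1.0 | 1.0 | 0.5 | 0 | 0.25 |

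Neither q nor s is in the documents. Chronic-antibiotic patients push q upward by an unknown amount.

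**5. Between arms.** Both arms have the same kit instruction, lead-in and stop, and the baseline sample is due by the week 0 visit at which patients are randomised. The expected difference in q is 0, and so is the expected bias. With q = 0.5 and 10 per arm, the chance difference in shares has SD √(2×0.25/10) = 0.22, or 22 percentage points. A 6-versus-4 split is 20 points. Even at s = 1.0 it moves the arm difference by 0.2×1.0 = 0.2 SD, against a standard error of √(2/10) = 0.45 SD (taking the SD of change as 1).

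**The case against.** The strongest reply is that this is a randomised trial with a shared lead-in, that the measures are listed as exploratory, and that the pre-antibiotic stretch is short and open only to some patients. Concomitant medication is recorded at screening and week 0, so antibiotic exposure is documented. Choosing a pre-antibiotic or an end-of-lead-in baseline is a matter of judgement.

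Much of this stands. Several stronger conclusions that a reader might draw do not hold:

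- *The FMT-versus-placebo comparison is biased.* It is not, in expectation. A modest chance imbalance between arms of 10 is within ordinary noise.
- *A pre/post significance test will be run on these markers.* The Wilcoxon test in the Section 1 summary is specified for mPDAI total scores and subscores only.
- *Engraftment is measured from this sample.* Section 20 uses the donor similarity index to follow engraftment over time; it is not defined as a change from the recipient's baseline.
- *An on-antibiotic baseline would isolate the FMT effect.* It would make the antibiotic state uniform, but each change would then combine FMT with antibiotic withdrawal.

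What the reply leaves open is the within-patient and pooled summaries. The short pre-antibiotic stretch is little comfort, because Section 5 names the screening visit as the collection time for calprotectin. Medication records do not help unless the stool's collection date is also recorded, and the plan does not ask for it.

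**Conclusion.** The point holds as a cheap improvement. As written, the sampling rule lets active-pouchitis entrants who are not already on antibiotics contribute baselines in different treatment states, while chronic-antibiotic patients contribute on-treatment baselines. Changes in calprotectin and before/after microbiome summaries, especially over all 20 subjects, can therefore carry part of the lead-in antibiotic's effect.

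The size cannot be taken from the documents. With half of baselines on antibiotics and an assumed shift of 0.25 to 1.0 SD, mean change moves by 0.125 to 0.5 SD. It would be zero if every baseline were on treatment. A comparison by randomised arm stays unbiased in expectation and only loses precision.

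**What to change.** 1. In Sections 5, 7 and 8, set one collection window for the calprotectin/microbiome baseline. The last 3 days before week 0 would match the mPDAI baseline in Section 19 and fits the existing return of the kit at week 0.
2. Keep C. difficile collection at screening. It is a separate component of the kit, and its result decides eligibility.
3. Record the collection date and the antibiotic status at collection.
4. In Section 20, report calprotectin and microbiome changes by randomised arm. This is needed even with a fixed window, because pooled changes from a uniform on-antibiotic baseline still mix antibiotic withdrawal with FMT.

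The cost is wording and two data fields. Entrants with active disease would have no pre-antibiotic calprotectin value, and separating the C. difficile collection may mean a second stool collection for some patients. If the team wants both states measured, one further sample per patient adds 20: 113 + 20 = 133 on the plan's own products, or 122 + 20 = 142 on the schedule it describes.
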